Among women with breast cancer who undergo neoadjuvant chemotherapy, complete pathologic response is a predictor of long-term outcomes across and within many subgroups variously defined by intrinsic subtypes, stage, grade, and nodal status [24-26]. In a meta-analysis, Gluck and colleagues pointed out an exception; among women with early-stage luminal A breast cancers, prognosis was not predicted by pathological complete response [27].

A recent meta-analysis gathered results from studies of immune infiltrates in breast tumors from patients who subsequently underwent neoadjuvant cancer therapies, and its findings confirm that

IRB # 204897 Site: UAMS Version 5 06/07/2019

immune infiltrates in pre-treatment breast tissue, and CD8+ infiltrates in particular, are predictive of pathologic complete response in many, but not all of the distinct breast cancer subtypes, including luminal A breast cancers ; *her2*+ breast cancers [28]; and basal breast cancers [24]. CD8+ immune infiltrates have been also observed to predict recurrence-free survival, breast cancer specific survival, and overall survival in breast cancer patients treated surgically prior to hormonal or chemotherapies [24]. Similar associations have been observed in studies looking at early stage breast cancers [25] and advanced breast cancers ; in patients receiving different anticancer therapies, including first-line chemotherapies [26], rescue chemotherapies, immune therapies and endocrine therapies; and in studies with different endpoints, including recurrence-free survival, overall survival and breast cancer specific-mortality.

We hypothesize that some of the heterogeneity in treatment outcomes may be explained by variations in systemic immune response and its determinants, including the gut microbiome. Therefore we are proposing a pilot study to evaluate feasibility of the proposed measures and to estimate parameters that will aid in planning a larger study designed to test the hypotheses that the gut microbiome can modulate the efficacy of neoadjuvant chemotherapies to treat breast cancer.

SPECIFIC AIMS

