Bioinformatics: Reads will be filtered through the Institute of Genome Sciences bioinformatics pipeline [15]. Operational taxonomic units (OTUs) will be defined using the Quantitative Insights Into Microbial Ecology (QIIME) pipeline as sequences with at least 97% identity, rarified (randomly sampled with replacement) to the minimum number of observed OTUs. Using the Ribosomal Data Project Bayesian classifier in QIIME, OTUs will be assigned to phylum, class, order, family, and genus level-taxa, and their relative abundances will be calculated [16]. Additional microbial measures of interest include alpha diversity (Shannon index, Inverse Shannon), beta diversity (UNIFRAC distances), and phylogenetic diversity (whole tree phylogenetic diversity), as measured using QIIME after using rarefaction to account for differences in amplification across fecal samples [16]. In addition, we would like to consider as exposures phylogenetic composition, assessed down to the levels of phylum, family, and genus. Finally, we will use the programs PICRUSt and Lefse to generate metagenomic data and measures of KEGG pathway abundances from phylogenetic profiles [17].

Characterization of immune response

Breast tissue collection: Tissue-based measures of immune response will require formalin-fixed paraffin-embedded tissues from primary tumor samples. After informed consent is

IRB # 204897 Site: UAMS Version 5 06/07/2019

obtained, archival tissue from a pre-treatment biopsy of primary breast tumor, in the form of a FFPE tissue block or pre-cut slides will be requested either from the diagnosing center or from the Tissue Biorepository. *Four* slides will be received or cut from formalin-fixed paraffinembedded tissues from primary tumor samples collected prior to chemotherapy. Slides will be prepared from an FFPE tumor tissue block of at least 5-µm thickness. An H&E slide will be scanned using an Aperio slide scanner and will be used to characterize the sample in terms of tissue composition (cell density, relative abundance of stromal, epithelial, and adipose cells). We will stain slides for T-lymphocytes and microenvironmental cues using antibodies for CD8, CD4, FoxP3, and PDLM1 using standard methods for cell surface markers and intracellular markers as described in the following reference [30].

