The Principal Investigator will carefully monitor study procedures to protect the safety of research subjects, the quality of the data and the integrity of the study. All study subject material will be assigned a unique identifying code or number. Data obtained during the study will be entered into C3PR and OpenClinica located in the UAMS clinical trial management suite. C3PR is a cancer Biomedical Informatics Grid (caBIG®, NCI) application that will keep a list of subjects

IRB # 204897 Site: UAMS Version 5 06/07/2019

enrolled and specific information regarding their enrollment. Data will be entered into OpenClinica through electronic web-based case report forms (CRFs). OpenClinica is a secure open source system for electronic data capture and clinical data management. Data from OpenClinica can be easily extracted for analysis throughout the study.

After informed consent is obtained, the data will be collected, coded with a study ID number, and stored indefinitely.

Data Analysis

Analyses will be conducted according to study aims. As the aims are considered exploratory, P values < 0.05 will be considered statistically significant and no adjustments will be made for multiple comparisons.

Aim 1. To assess the acceptability and feasibility of study procedures.

We will describe numbers and characteristics of women who are 1) screened, 2) eligible, 3) consented, and 4) complete collections for each type of biospecimen. In a brief form which will accompany the fecal sample, we will ask enrolled women specifically about the acceptability of, and logistical difficulties with, the procedures for collection and packaging of the fecal specimen.

Aim 2. To estimate proportions of patients with pathological complete response by host factors, breast cancer subtypes, tumor characteristics, reported gastrointestinal symptoms, and by categorical measures of gut microbial composition, diversity, and metabolic activity.

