We will estimate and compare rates of pCR by each factor using chi-squared tests for crude comparisons and multivariable logistic regression for adjusted comparisons. Factors of interest will include host factors such as age and menopausal status; and tumor characteristics including: intrinsic subtype assessed using clinically indicated measures (ER and PR status, Her2/neu status, and Ki67 positivity); standard clinical prognostic indicators (TNM stage and histologic grade), and subgroups defined using tertiles of all continuous gut microbial measures.

Aim 3. To estimate the associations of pre-treatment gut microbial composition, diversity, and metabolic activity with anticancer immune responses, measured as relative abundance of immune infiltrates in pre- treatment FFPE breast tumor tissues, and as relative abundance of circulating immune cell subtypes (Th1, Th2, Th17, and Treg) in baseline and longitudinal blood samples. Bivariate and covariate-adjusted associations among measures will be evaluated using Spearman's rank test and General Linear Models, respectively.

Aim 4. To estimate associations of the measures of local and systemic immune responses with host factors such as age, BMI, and smoking status, and with measures of the breast microenvironment including mammographic density and benign parenchymal enhancement on breast MRI. Bivariate and covariate-adjusted associations among measures will be evaluated using Spearman's rank test and General Linear Models, respectively.

Power and Sample Size:

Aim 1: If we screen 60 potential participants, we should be able to estimate, with 95%

IRB # 204897 Site: UAMS Version 5 06/07/2019

confidence, the true proportion of this patient population willing to participate in the study with precision of +/- 20%.

Aim 2: If 40 participants are enrolled and complete study measures, and the expected pCR in the category with the greatest risk of mortality is assumed to be 20%, then we will have 47% power to detect a statistically significant trend in rates of pCR across tertiles of microbiome measures if the odds ratio for the highest tertile is 5.0.

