Aim 3 and 4: If we have 20 participants with both tumor infiltrate measures and measures of gut microbial composition, we will have adequate power (β =80%) to detect relationships between the dependent variable (relative abundances of tumor infiltrating lymphocytes and circulating lymphocytes) and the independent variables gut microbial composition, diversity and metabolic activity; host factors, and measures of the tumor microenvironment) at a two-sided α =0.05 significance level, when the true change in the dependent variables is 0.67 standard deviations per one standard deviation change in the independent variables.

Ethical Considerations

This study will be conducted in accordance with all applicable government regulations and University of Arkansas for Medical Sciences research policies and procedures. This protocol and any amendments will be submitted and approved by the UAMS Institutional Review Board (IRB) to conduct the study. In addition, all study personnel must have completed human subject protection training.

The formal consent of each subject, using the IRB-approved consent form, will be obtained before that subject is submitted to any study procedure. All subjects for this study will be provided a consent form describing this study so they can make an informed decision about their participation in this study. The person obtaining consent will thoroughly explain each element of the document and outline the risks and benefits, alternate treatment(s), and requirements of the study.

The consent process will take place in a quiet and private room, and women may take as much time as needed to make a decision about their participation. The privacy of all subjects will be maintained and questions regarding participation will be answered. No coercion or undue influence will be used in the consent process. This consent form must be signed by the subject and the individual obtaining the consent. A copy of the signed consent will be given to the participant, and the informed consent process will be documented in each subject's medical record.

Dissemination of Data

Results of this study may be used for presentations, posters, or publications. The publications will not contain any identifiable information that could be linked to a participant.

References

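### The rarefaction depth is written as a count of OTUs instead of a count of sequence reads: probably a wording slip, with a small effect if followed literally

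*Combined protocol and SAP*

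**What the plan says.** In the combined protocol and SAP, the Bioinformatics paragraph under Microbial DNA assays describes OTUs "as sequences with at least 97% identity" and continues, in the same sentence, "rarified (randomly sampled with replacement) to the minimum number of observed OTUs". Two sentences later it gives the purpose: the diversity measures, including the Shannon index, are taken "as measured using QIIME after using rarefaction to account for differences in amplification across fecal samples". No read count, numeric depth or rule for low-yield samples appears anywhere in the document.

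These measures are then used as exposures. Data Analysis, Aim 2, compares pCR rates across "subgroups defined using tertiles of all continuous gut microbial measures". Aim 3 relates them to immune measures. The Background says that the pilot is to "estimate parameters that will aid in planning a larger study". Data Analysis opens its rule on significance testing with "As the aims are considered exploratory".

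**The concern.** A rarefaction depth is the number of reads drawn from each sample so that all samples are compared at equal sequencing effort. The number of OTUs observed in a sample is its richness, which is a biological property of the sample and not a measure of sequencing yield. It cannot exceed the read count and is usually far below it. The stated depth is therefore in the wrong unit for its stated purpose.

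If an analyst followed the sentence literally, each sample would be cut to a few dozen or a few hundred draws. Shannon diversity from so few draws has more random error and is biased downward. Random error moves women between tertiles in Aim 2 and pulls associations towards the null in Aims 2 and 3. The downward bias would distort the diversity values passed on to the larger study.

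**Working it through.** **What can be reproduced.** The plan gives no depth, so there is no depth figure to reproduce. The one related figure is the 80% power for Aims 3 and 4, with 20 participants and a slope of "0.67 standard deviations per one standard deviation change in the independent variables". Taking a residual SD of 1 and the noncentral t distribution, the noncentrality is 0.67 × √20 = 3.00 and power is 0.81, so the stated figure reproduces.

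**Noise and bias of Shannon.** The assumed inputs are log-normal communities of 150, 300 or 600 OTUs, log-SD 1.5, 2.0 or 2.5, and 1,000-4,000 or 3,000-10,000 reads per sample. That makes 18 settings, each with 120 simulated samples and 60 redraws per sample. Both depths were drawn with replacement:

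| | Minimum OTU count (literal) | Minimum read count |
|---|---|---|
| Depth (draws) | 22-326 | 1,000-3,219 |
| SD of Shannon between redraws | 0.067-0.224 | 0.024-0.052 |
| Bias of Shannon | -0.54 to -1.35 | -0.03 to -0.34 |
| Correlation with true Shannon | 0.884-0.986 | 0.988-0.999 |

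The literal depth was noisier in all 18 settings, by a factor of about 1.9 (0.075/0.040) to 8 (0.224/0.028). Drawing without replacement at both depths gave the same direction.

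**Tertile misplacement.** The assumed inputs are 40 women, 200 or 600 taxa, 1,000-5,000 or 3,000-30,000 reads per sample, and several spreads of abundance, making 24 settings. Truth is the Shannon index of the composition before sequencing. The literal depth was 41-391 draws (0.5-10% of reads), against 1,031-3,243 (27-43%) at minimum read depth. Women in the wrong tertile:

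- literal depth, one draw: 13-26% (0.13 × 40 ≈ 5 to 0.26 × 40 ≈ 10 women)
- minimum read depth, with replacement, one draw: 3-18% (about 1 to 7 women)
- minimum read depth, without replacement, one draw: 2-13% (about 1 to 5 women)
- literal depth, average of 30 draws: 4-13% (about 2 to 5 women)

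**Consequence for Aim 2 (illustration: literal reading, single draw).** The power statement refers to a "trend in rates of pCR across tertiles of microbiome measures if the odds ratio for the highest tertile is 5.0". Assume that this ratio holds for true Shannon tertiles, that the plan's 20% pCR belongs to the lowest tertile, and that the middle odds ratio is √5 = 2.24. Odds of 0.25, 0.56 and 1.25 give pCR of 20%, 35.9% and 55.6%. The pCR in an observed tertile is the sum over true tertiles of (share of women from that true tertile × its pCR). The resulting top-versus-bottom odds ratio is 3.5-4.2 under the literal rule. At minimum read depth it is 4.0-4.8 with replacement and 4.3-4.9 without. Averaging 50 draws at the literal depth gives 4.2-4.7.

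For scale, take 14 and 13 women in the outer tertiles. The SE of the log odds ratio is √(1/2.8 + 1/11.2 + 1/7.22 + 1/5.78) = 0.87, so the 95% interval around 5 is exp(1.609 ± 1.96 × 0.87), about 0.9 to 28.

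**Consequence for Aim 3 (illustration: literal reading, single draw).** The expected slope is 0.67 × r, where r is the correlation of observed with true Shannon in the 24 settings. Literal rule: 0.67 × 0.921 = 0.62 to 0.67 × 0.985 = 0.66. Minimum read depth without replacement: 0.67 × 0.986 = 0.66 to 0.67 × 1.000 = 0.67. With residual SD √(1 + 0.67²(1 − r²)), power for a Shannon exposure is about 0.71-0.79 under the literal rule, against 0.81 without error.

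**The case against.** The strongest reply is that the sentence is harmless in context. It describes OTUs as sequences, so the observed OTUs being sampled may simply be OTU-assigned sequences, and the stated purpose points the same way. This stands: it is the likelier reading, and on it only the wording needs correcting.

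A second reply is that the simulated size depends on one draw per sample, which the plan does not specify. This also stands. Averaging draws brings tertile misplacement close to what read depth gives. It does not remove the downward bias, because the average of low values is still low.

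A third is that part of any improvement could come from dropping replacement rather than from changing the depth. Both versions are therefore shown above. The change of depth accounts for most of the difference, and replacement for a smaller part.

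Finally, the methods papers that the protocol cites may give an operating depth. They cannot be checked here, and they would not alter what the protocol itself says.

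A reader might infer more: that the diversity analyses will be run on a few dozen reads, or that up to a quarter of the women will be misclassified. The documents do not support this. They contain no read or OTU counts, do not say that a single draw is used, and state a purpose that fits a depth in reads.

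**Conclusion.** The plan's only statement of rarefaction depth is in the wrong unit for its own stated purpose. That much follows from the text alone. Whether any result would be affected is uncertain, and probably none would be.

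Under the literal reading with one draw, the direction is firm: Shannon becomes noisier and lower. The size rests on assumed read counts, taxa counts and abundance spreads. The tertile, odds-ratio and slope figures are illustrations of that reading only and concern Shannon only. Even then, the shift in the Aim 2 odds ratio is small beside an interval of roughly 0.9 to 28 and a stated power of 47%, and the change in the Aim 3 slope is slight. The aims are exploratory, and the depth can be corrected at analysis without new samples. Severity: minor.

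**What to change.** In the Bioinformatics paragraph, replace "rarified (randomly sampled with replacement) to the minimum number of observed OTUs" with: *rarefied (randomly sampled without replacement) to the minimum number of sequence reads per sample among retained samples*. Changing the depth alone would leave sampling with replacement in place, which adds avoidable noise at read depth (3-18% in the wrong tertile, against 2-13% without replacement).

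Optionally, state in advance the minimum read count for retaining a sample. This is good practice, but it does not follow from the error in unit.

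The cost is one sentence of text. The small downside is that a very low-yield sample would set the depth for everyone, so it may have to be excluded or re-run.

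### Rarefaction with replacement leaves a residual dependence on read depth in richness-type microbiome measures; the sentence needs both the sampling method and the depth corrected

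*Combined protocol and SAP*

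**What the plan says.** The Bioinformatics paragraph (combined protocol and SAP, Microbial DNA assays) defines OTUs "as sequences with at least 97% identity". It then says they are "rarified (randomly sampled with replacement" and gives the depth as "to the minimum number of observed OTUs". That depth is a count of taxa, not of reads, and no number is attached.

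The same paragraph lists the measures computed afterwards: "alpha diversity (Shannon index, Inverse Shannon), beta diversity (UNIFRAC distances), and phylogenetic diversity (whole tree phylogenetic diversity". They are obtained "after using rarefaction to account for differences in amplification across fecal samples", which is the stated purpose of the step. The form of UniFrac (weighted or unweighted) is not given.

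Under Data Analysis, Aim 2 compares pathological complete response across "subgroups defined using tertiles of all continuous gut microbial measures". Aim 3 relates pre-treatment microbial composition, diversity and metabolic activity to immune measures, using Spearman's test and general linear models. No other section changes the sampling method, and no number of draws or sensitivity analysis is specified.

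**The concern.** Rarefaction puts samples with different read yields on a common footing. If *m* reads are drawn without replacement from each sample, the expected number of OTUs no longer depends on how deeply that sample was sequenced. If they are drawn with replacement, each sample's observed reads are resampled a second time. A sample at or near the common depth then loses rare OTUs to duplicate draws, while a much deeper sample hardly notices. Two women with the same gut community but different yields can therefore receive different richness values, which is what the step was meant to prevent.

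At stake is how women are ordered on the richness-type exposures. Aim 2 uses tertiles and Aim 3 uses ranks, so a yield-related shift can move women who lie near a cut-point.

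**Working it through.** **Inputs.** From the plan: sampling with replacement, a depth stated as the minimum number of observed OTUs, and 40 women expected to complete the study (Study Population). Not in the plan, so assumed: reads per sample, number of OTUs and spread of abundances. The plan gives no rarefaction figure to reproduce.

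**Step 1: formulas.** For a sample with *N* reads, OTU counts *c*, and *m* reads drawn, the expected number of OTUs is
- without replacement: Σ[1 − C(N−c, m)/C(N, m)]
- with replacement: Σ[1 − (1 − c/N)^m]

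Under either scheme the expected share of an OTU in the draw is c/N, so expected relative abundances are unbiased.

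**Step 2: mechanism.** In the shallowest sample, with m = N, an OTU with *c* reads is lost with probability (1 − c/N)^N ≈ exp(−c). That is 0.37, 0.14 and 0.05 for c = 1, 2, 3; without replacement nothing is lost. For m = 3,000, a singleton is kept with probability:

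| Reads in sample | With replacement | Without |
|---|---|---|
| 3,000 | 0.632 | 1.000 |
| 6,000 | 0.393 | 0.500 |
| 15,000 | 0.181 | 0.200 |
| 30,000 | 0.095 | 0.100 |

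The shortfall due to replacement shrinks quickly as depth increases.

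**Step 3: one community sequenced at two depths.** The true difference is zero, so any gap is read-depth bias. Example with 500 OTUs, log-normal abundances (log SD 2), and 3,000 against 30,000 reads:

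| | OTU gap | Shannon gap (nats) |
|---|---|---|
| No rarefaction | 56.2% | 0.0655 |
| With replacement, m = minimum reads | 14.6% | 0.0453 |
| With replacement, m = minimum OTUs | 2.8% | 0.0183 |
| Without replacement, m = minimum reads | 0.0% | 0.0006 |

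Twelve scenarios were run (300–1,000 OTUs, log SD 1.5–2.5, lowest depth 1,000–10,000 reads, tenfold contrast). With replacement at the minimum read count, the OTU gap is 3.8–24.2%, which is 12–58% of the unrarefied difference in OTU number. At the literal OTU depth it is 0.6–8.0%. Without replacement at the minimum read count it is −0.3% to +0.5%. For Shannon, 51–97% of the unrarefied gap remains at the minimum read count, but that gap is itself small (0.014–0.253 nats, or 0.3–5.4%).

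**Step 4: 40 women with differing communities.** Assumed: 300–500 OTUs, median 2,000–5,000 reads, log SD of reads 0.3–0.8.

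| Sampling and depth | Spearman correlation, richness vs reads | Top vs bottom depth tertile |
|---|---|---|
| With replacement, minimum reads | 0.28–0.34 | 6–8% |
| With replacement, minimum OTUs | 0.04–0.07 | about 1–2% |
| Without replacement | about 0 | about 0 |

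For Shannon the correlation is 0.07 or less throughout. Other assumed communities change the size but not the direction. One set, in which raw richness correlated 0.33–0.78 with reads, gave 0.12–0.23 at the minimum read count and 0.01–0.04 at the literal depth. Another, with minimum depths of 1,000–5,000 reads and log SD of depth 0.3 or 0.6, gave a tertile gap of 4.0–6.5%.

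**The case against.** The strongest reply is that the larger figures do not describe the plan as literally written. They need a depth equal to the minimum read count, whereas the plan names a number of OTUs. At that much smaller depth the two sampling schemes nearly coincide: in simulation, switching scheme changed tertile membership about as often (38–41% of women) as repeating the draw without replacement did. This stands. It means that changing the one word alone would achieve little, and that the depth must be corrected in the same edit.

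It is also fair that this is an exploratory pilot with a stated 47% power for Aim 2. Unless read yield is related to response or to immune measures, the residual acts as noise rather than as bias in the associations. Nothing in the documents suggests such a relation.

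Three stronger readings are tempting, and the documents do not support them:
- *Rarefaction fails and all microbial exposures stay tied to yield.* Most of the richness gap is removed, Shannon barely tracks yield between women, and expected relative abundances are unbiased.
- *Post-chemotherapy samples will look falsely less diverse.* That would need lower yield after treatment, which no section suggests. No pre/post diversity comparison is specified, and Aim 3 uses pre-treatment measures.
- *Presence of rare genera is distorted as an exposure.* The plan specifies relative abundances of taxa, not presence or absence.

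The phrase may be a slip of wording. The documents do not show that, and if it is one, the text should still match what will be run.

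**Conclusion.** The point holds in limited form. The stated sampling method works against the purpose given for it, and no other section overrides it. What survives is a residual dependence on read depth in richness-type measures. Whole-tree phylogenetic diversity is the one clearly affected measure that the plan names; UniFrac joins it only if the unweighted form is used.

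The size is conditional on read depths, OTU numbers and between-woman variation that the documents do not give. Under the Step 4 assumptions it is moderate for a read-based depth and close to negligible for the literal OTU depth. For a pilot meant to supply planning parameters for a larger study, this is a modest and avoidable source of noise or bias in the Aim 2 and Aim 3 diversity exposures. It does not threaten the study.

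**What to change.** Rewrite the sentence in one edit: *randomly sampled without replacement to the minimum number of reads per sample*. State that number once the read counts are known, and average the diversity measures over repeated draws. Stating which form of UniFrac will be used would also settle whether it is affected.

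The cost is a pipeline setting, a little computing for the repeated draws, and a wording change that needs IRB approval under the section on protocol modifications. No new samples, visits or participants are needed.
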